3.3.2 Consent of participants living in their own homes

The participant invitation letter will advise potential participants that if they are happy to take part in the study and do not require any further information, they can sign the enclosed consent form and return it in the envelope provided or they can visit the study website to complete the consent form online.

The invitation letter will also advise that if they would like more information or are not able to return the consent form by post, they can call the Clinical Research Network to discuss further and have their consent taken over the telephone. This will provide participants with the opportunity to ask questions before deciding. The CRN have agreed to support this activity. However, if for capacity reasons they are not able to provide resource to do this at the time recruitment begins, GP practices will be asked to support this activity instead and the Participant Invitation Letter / PIS will be updated accordingly before being sent out.

The participant consent form has been submitted as part of this application and will ask the participant to consent that they:

- have read and understood all the information about the study and have had all your ٠ questions answered satisfactorily
- taking part is voluntary and you can stop taking part at any time without this affecting your medical care or legal rights in anyway
- understand we will not intervene in your usual care while you are taking part in the study
- members of the Research Team will read relevant sections of your medical history and that you give permission for the Research Team to access this information
- understand that the information collected about you will be used to support other research in the future and may be shared anonymously with other researchers

Commented [CP2]: I think we say indefinitely elsewhere in the documentation although I'm not sure if this is acceptable - other studies are destroying them some time after the

13

IRAS ID: 286225 [Proof of Concept – Smart Technology – South Lincolnshire] CPMS: 44344 PoC Protocol Version: 1.4

01/08/2020

- agree for your GP to be involved in this study and that necessary information about you will be exchanged between your GP and the Research Team
- understand the information held by the researchers may be used to contact you but only while you are taking part in the study
- agree to take part in the study and undertake the required study activities (i.e. take your own health readings and/or wear a comfortable Smart Device over the period of the study which will securely record data about your health)
- are happy for your data to be collected, used, shared and stored as described in this information sheet
- understand you will not gain any particular benefit from taking part, but may be helping others in the future

Consent forms will be returned by post to Optima Systems. Optima Systems are responsible for generating the unique ID number for you for the purposes of the research. This ensures that all the data collected from participants will be pseudonymised.

Optima Systems will call the participant upon receipt of their consent forms to check all the information provided is correct and undertake a technical assessment to establish which equipment needs to be sent to the participant. Although device will be allocated at random, the research team will need to understand the connectivity and infrastructure available.

Optima Systems will then inform the participants GP that they have been onboarded to the study and ask the GP practice to cross check the information collated on the consent form to ensure that only invited participants are included. This will also help GP practices manage recruitment lists and remove anyone who has not consented from the study and any future recruitment rounds.

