3.2 Participant selection

3.2.1 Participants living in their own homes

The research team will work with the CCG and Commissioning Support Unit (CSU) to identify suitable patients to be approached to take part in the study from pseudonymised NHS patient data.

This will involve using data analysis algorithms called the Diagnostic Stratification Technique, which has been developed by Helicon and their partner i5Health. It is based on Machine Learning, Neural Networks and Artificial Intelligence to analyse millions of clinical patterns from de-identified patient data collected by the NHS in the Hospital Episode Statistics (HES) database. HES comes from data collected by NHS Digital to provide CCGs and care providers with important information pertaining to commissioning and payment for care delivered to patients. However, it is also possible to use this data for research purposes and other secondary uses. This is because strict statistical disclosure control is applied in accordance with the NHS Digital protocol, which suppresses small numbers to stop individuals being identified from the data and ensure patient confidentiality is maintained.

The CCG will formally request Helicon and i5Health to undertake a search for their HES data to produce a list of pseudonymised patients. This list will then be passed to the CSU Data Services for Commissioning Regional Offices (DSCRO) for re-identification. This will ensure that all Information

11

Governance (IG) requirements are strictly applied. Once re-identification is complete, the CSU will be able to group patients into lists according to their registered GP practice. These lists will then be securely distributed (using NHS mail or other secure connection) to the relevant GP practices so that the participant recruitment process can begin. It is important to note that no party other than the CSU and GP practice will be able view the identifiable patient data at any point prior to formal consent being obtained from the patient directly.

Once each GP practice has a list of potential participants, GPs or healthcare professions will be able to review each patient record individually in line with the study's inclusion / exclusion criteria to make further exclusions where appropriate.

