3.3 Participant recruitment and consent

3.3.1 Recruitment of participants living in their own homes

The study intends to recruit 500 participants to take part in the study and will therefore aim to invite at least 700 to individuals to participate.

To do this, the research team will provide GP practices with the following participant facing documents to use in recruitment activities with their own patients:

1. Participant Invitation Letter

This will give a brief summary of the study and instructions on how to either accept or decline the invitation.

2. Participant Information Sheet (PIS)

This will provide a more detailed explanation of the study including what the participant will need to do, why we are undertaking the study, how they can withdraw from participation etc. a copy of the PIS has been submitted with this application.

3. Study Consent Form

This will be the formal consent form that participants will sign to agree to take part in the study. Due to Covid-19, consenting processes have been adapted to ensure that consent is undertaken remotely. The Clinical Research Network have confirmed that the consent form can be posted to participants as part of the initial communication. Prior to Covid-19, consent would have been obtained in a face to face meeting with a healthcare professional. Please see section 3.3.2 below for full details).

12

IRAS ID: 286225	[Proof of Concept – Smart Technology – South Lincolnshire]
CPMS: 44344	PoC Protocol Version: 1.4
01/08/2020	

4. Text Message Content

A follow up text message will be sent to those potential participants who have a mobile number recorded with their GP practice. It will refer them to the study pack sent in the post and include a link to the cloud environment where they can securely complete their consent form online.

The GP practice will send the information pack above to each potential participant and include a prepaid return envelope addressed to Optima Systems Ltd for them to return their signed consent forms. The invitation letter will also include a URL where participants can complete their consent form electronically online if they prefer. Optima Systems Ltd will collate and store signed consent forms for a period of XXXXXX

The participant will be given three options:

- 1. Sign and return the consent form if they are happy to take part (either online or by post)

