3.4 Participant onboarding

3.4.1 Allocation of devices

Once participants have provided their consent, each will receive a phone call from Optima Systems Ltd to:

- Ensure the information provided is correct
- Check that the participant is still happy to proceed
- Reiterate the key points of information provided in the Participant Information Sheet
- Establish the current technical capability of each participant i.e. WiFi connectivity

We intend to choose the most suitable smart technology for each patient. The choice of the smart technology is based on careful judgement and we will aim to develop an approximate "right app or wearable for the right patient" as clearly as we can. We will do this based on the initial conversation held with the participant.

Since patients do not necessarily become ill with the same conditions they already have, one or at most two devices per patient will be chosen. We are aiming to include about a third of the patients from residential and care homes since they will tend to be more vulnerable and more likely to have an adverse health event and certain apps can be used by smart devices can be installed from the internet.

The questionnaires will be sent and completed by the patient on the smart phone, tablet or desktop. We currently are considering how we can safely use the same tablet in a Care home to obtain clinical information on respiratory and heart rate and BP oxygen saturation on several patients. This will involve engaging with the residential and care home staff to develop safe procedures; this will be helped by the knowledge of the Covid-19 status of both patients and staff in terms of blood antibody tests on all the staff and all the patients. We hope also that the availability of PPE (Personal Protective Equipment) will be confirmed in each of the relevant homes.

The next action will be to arrange for the participants to receive the wearable or smart technology and to be shown how to use it by the "research supporter" with the aid of the internet. We will be allocating participants randomly according to their circumstances, to receive two (or at most three) wearables or smart technologies.

Commented [CP3]: Updated slightly as we have concluded device allocation will be random to an extent – please ensure my wording is accurate here

Commented [**CP4**]: I think we should go further here and propose a process otherwise it is quite a big question mark this will link back to the SOP you are developing [name].

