This will be the formal consent form that participants will sign to agree to take part in the study. Due to Covid-19, consenting processes have been adapted to ensure that consent is undertaken remotely. The Clinical Research Network have confirmed that the consent form can be posted to participants as part of the initial communication. Prior to Covid-19, consent would have been obtained in a face to face meeting with a healthcare professional.

4. Decline to Participate Return Slip

This will allow a participant to advise the GP practice if they do not wish to take part in the study.

The GP practice will send the information pack above to each potential participant and include a prepaid return envelope for them to return their signed consent form or decline to participate return slip.

The participant will be given three options:

- 1 Sign and return the consent form if they are happy to take part
- 2 Sign and return the *Decline to Participate Return Slip* if they do not wish to take part
- 3 Wait for a telephone call from the GP practice if they require further information before deciding

Patients will then be given one week to decide whether they want to take part before further contact is made with them. After a week has passed, a healthcare professional from their GP practice will call them to discuss the study and if the patient is still unsure, they will be given longer to consider.

More detailed descriptions of the consenting processes is contained in the Consent and Patient Information Sheet (PIS). It will be made very clear to the participants that:

- a) their usual care will continue as usual if they agree to join PoC;
- b) they will not gain any particular benefit for themselves in health terms but they will be helping others. They will understand that they understand that the PoC is an "observational study";
- c) there will be support on offer to them during the trial by messaging electronically, or by phone and speaking to one of our helpers;
- d) they can withdraw from the trial at any time without the need to give a reason; their pseudonymised data cannot be removed and will continue to be used;

27

IRAS ID: 286225[Proof of Concept – Smart Technology – South Lincolnshire]CPMS: 44344PoC Protocol Version: 1.401/08/2020

- e) should they become unwell and lose capacity they will not continue in the research study but their pseudonymised data will be retained and used in the study;

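### For own-home participants, the GP check that a consenting person was invited comes after onboarding, so it can detect an uninvited, unscreened entrant but cannot keep them out

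*Protocol*

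**What the plan says.** Section 3.2.1 has the GP practice receive a list of its potential participants and "review each patient record individually in line with the study's inclusion / exclusion criteria to make further exclusions where appropriate". It adds that "no party other than the CSU and GP practice will be able view the identifiable patient data at any point prior to formal consent" is obtained.

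Section 3.3.1 sends the study pack from the practice, with a reply envelope addressed to the onboarding contractor. It also offers an online route: "The invitation letter will also include a URL where participants can complete their consent form electronically online if they prefer". A text-message link and telephone consent are available too.

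Under Section 3.3.2 the contractor generates the study ID, telephones the person to check their details and assess the equipment needed, and then contacts the practice: "Optima Systems will then inform the participants GP that they have been onboarded to the study". In the same sentence it will "ask the GP practice to cross check the information collated on the consent form to ensure that only invited participants are included".

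Section 3.4.1 lists what the contractor's call covers. One item is "Check that the participant is still happy to proceed"; the others are correctness of the details, a reminder of the key information and technical capability. It then names supply of the technology as the next action.

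Section 6, item (d), says of people who withdraw that "their pseudonymised data cannot be removed and will continue to be used". Item (e) provides for retention after loss of capacity.

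**The concern.** The stated purpose of the GP step is that only invited people are included. A step with that purpose has to come before inclusion. Here it is requested when the practice is told that inclusion has already happened.

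The order matters because, on this route, being invited stands in for having been screened. Section 3.1 excludes people on palliative care, people who lack capacity and people whose mental health might be influenced by taking part. For own-home participants those exclusions are applied in the pre-invitation record review and nowhere else that the protocol describes. A person who consents without having been on the reviewed list (for example, someone else in the household who uses the form or link) has not passed through that review. At stake is whether such a person is given devices and recorded before anyone has looked at the exclusions.

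**Working it through.** No formula applies and the plan states no figure to reproduce. The check is to put the steps in order and ask at which one an uninvited person would be stopped.

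1. **Record review, Section 3.2.1.** Exclusions are applied to listed patients only. Someone not on the list is not reviewed.
2. **Consent, Sections 3.3.1 and 3.3.2.** The form reaches the contractor by post or online, or consent is taken by telephone. No invitation code or match to the list is described for any of these routes.
3. **Study ID and call, Sections 3.3.2 and 3.4.1.** None of the listed call items asks about eligibility, the exclusions or invitation. Before consent the identifiable list is confined to the CSU and the practice, and no later transfer of it to the contractor is described. On the text, the contractor has nothing to check against.
4. **GP informed and asked to cross-check, Section 3.3.2.** This is the first point at which a consenting person is compared with the invitation list. By then the person is described as onboarded.
5. **Device supply, Section 3.4.1.** It is named as the next action after the call. The GP step is not mentioned there, so supply is not made conditional on the reply.

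Two other controls might have closed the gap:

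- The steering group's monitoring tool (Section 5.4) matches study number to device ID. It does not match a person to the invitation list.
- The NHS data extraction (Section 5.2) filters on the list of participating patients. That list would contain a wrongly onboarded person unless someone had removed them first, and no removal step is written. The follow-on use named in Section 3.3.2 is managing the practices' recruitment lists and removing people who have not consented. It does not say what happens to someone who consented without being invited.

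Size of the route: the target is 500, with about a third or fewer from care homes (Section 3.2.2). That leaves about 500 × (1 − 1/3) ≈ 333 own-home participants, or more if care-home recruitment falls short. This is the number passing through the step, not the number affected. The protocol gives no basis for a rate of uninvited responses.

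**The case against.** The strongest reply is that the check exists, that its stated purpose is to decide inclusion, and that the word onboarded may be loose. No section says that devices are dispatched or readings taken before the GP answers. Section 3.4.1 omits the GP step altogether, so it does not fix the order of dispatch and reply. This stands in part: recording before the reply is possible, not certain. But the only order the text does give puts the request after onboarding, and no hold is written anywhere.

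The reply also limits the consequences, and here it largely succeeds:

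- **Data that cannot be removed.** A reader might infer from Section 6 that an uninvited person's data would be locked into the data set. Items (d) and (e) concern withdrawal and loss of capacity among people properly enrolled. Neither covers someone found never to have been invited. How such data are treated is also commonly left to a statistical analysis plan, so the silence is not itself a fault.
- **Contaminated models.** A reader might infer that early readings would stay in the models. Section 3 rules out real-time analysis, and Section 5.2 joins device data to care records at the end of the study. A failed check would normally be known well before modelling.
- **Linkage to the wrong NHS record.** A mismatched identity is what the call and the cross-check are there to catch. A late check can still catch it.
- **Exposure.** The study is observational, readings are hidden from participants and usual care continues, so a short period of wrongful inclusion carries little described risk.

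Section 6 also describes a paper-based process with GP telephone follow-up, which sits uneasily with the online route in Section 3.3.1. If that version is the one used, the opening for uninvited responders is narrower. It still places no invitation check before onboarding.

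**Conclusion.** The point holds as a matter of sequence. The protocol's order does not deliver the purpose it gives for the step: the check can detect an uninvited, unscreened person but cannot prevent their being onboarded and possibly recorded. This rests on two readings: that onboarded means what Section 3.4 uses it for (device allocation, training and support), and that no invitation check happens at a step where none is described.

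The size is not given and is probably small, since packs go from the practice to patients whose records were open to review. The gain from correcting it is mainly in protecting people the protocol means to exclude. No bias in the predictive analyses is shown, and the protocol does not require an uninvited person's data to be kept. It is a cheap improvement.

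**What to change.** In Section 3.3.2, move the cross-check forward. The GP practice confirms that the consenting person is on its reviewed invitation list, with matching identity, before the study ID is activated and any device is sent. Make device supply in Section 3.4.1 conditional on that confirmation.

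Add one sentence saying that anyone who fails the check is not enrolled, and that any data already recorded from them are left out of the analysis. In Section 6, limit item (d) to withdrawal by properly enrolled participants, so that the two rules cannot be read against each other.

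The step and the people who carry it out are already in the protocol, so the cost is a short wait for the practice's reply before each own-home participant starts.

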3.3.3 Recruitment in residential care homes & nursing Homes

The care home manger / care home professionals will be responsible for recruiting and consenting their residents. No one from outside the resident's usual care team will visit the care home before or during the study.

After initial selection is completed as described above, care home professionals will speak to suitable residents to gauge their interest in taking part and provide them with the following study literature:

- Participant Invitation Letter (as above tailored to study processes within a care home setting)
- Participant Information Sheet (as above tailored to study processes within a care home setting)

Residents will then be given as much time as they need to consider taking part in the study; they will also be encouraged to discuss the study with friends or relatives. They will be asked to notify their care home manager or usual care home professional if they decide they are happy to participate.

3.3.4 Consent of participants living in residential or nursing care homes

Care home professionals will also be responsible for obtaining informed consent from its residents. Once a resident has expressed verbal interest in taking part in the study, the care home manager or care professional will meet with them to complete the consent form and provide further opportunity for residents to ask questions.

14

The consent form will be signed by both the resident and the person taking consent and a copy of the sign consent form will be given to the participant.

The details of consented participants will then be passed to Optima Systems. Optima systems will liaise directly with the care home manager / staff in order to provide equipment and onboard participants to the study.

The participants will be advised that we are not using face-to-face methods and pamphlets as a Covid-19 precaution. Instead we will use what we are calling "participant facing documents" to explain the study and will be encouraging questions, with the intent of ensuring that participants are fully informed in some detail.

